## **Study Drugs**

There are no new study drugs being used in this study. Per the FDA "SGLT2 inhibitors are a class of prescription medicines that are FDA-approved for use with diet and exercise to lower blood sugar levels in adults with type 2 diabetes. Medicines in the SGLT2 inhibitor class include canagliflozin, dapagliflozin, and empagliflozin" (18). In May 2020, the FDA approved dapagliflozin for use in HFrEF, regardless of diabetes status (19).

## **Study Subjects**

The study will include patients at UCMC who are admitted to the CCU by the advanced heart failure service after right heart catheterization for acute decompensated heart failure requiring vasoactive support.

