### **Study Design, Study Procedures, and Statistical Procedures**

This study is designed as a single center, prospective, randomized controlled study to assess cardiac benefit of SGLT2i in 40 consecutive patients (20 treatment, 20 control) admitted to University of Chicago Cardiac Intensive Care Unit (CCU) Advanced Heart Failure Service. Patients will be randomized to one of two routine care arms: treatment with an SGLT2i (dapagliflozin 10 mg daily) or no SGLT2i. Assuming a power of 80% and alpha of 0.05, 16 patients are needed in each arm of the study to detect a 5 mmHg change in pulmonary capillary wedge pressure (PCWP), and 18 patients are needed in each arm of the study to detect a 0.75 L/min/m^2 change in Fick cardiac index (CI).

Patients  $\geq 18$  years old, with heart failure with reduced ejection fraction (HFrEF), defined as left ventricular ejection fraction (LVEF)  $\leq 40\%$ , who are admitted to the CCU for acute decompensated heart failure and determined to need pulmonary artery catheter in place for continuous hemodynamic monitoring following right heart catheterization, will be included in this study. Patients listed for cardiac transplantation or on mechanical support will be excluded. Due to the inability to consent patients following sedation given during the right heart catheterization,

patients determined to have a high likelihood of needing CCU admission, based on individual clinical presentation, will be approached for recruitment and asked for informed, written consent. However, patients will only be enrolled if it is determined independently to admit the patient to the CCU with the pulmonary artery catheter in place. If determined to need CCU care with continuous pulmonary artery catheter monitoring, patients will then be randomized, in a 1:1 fashion using the random number generation function in Microsoft Excel, to either treatment with an SGLT2i (dapagliflozin 10mg once daily) or no SGLT2i. Therefore, we anticipate recruiting and consenting more than 40 patients, but we will only randomize and treat patients that fulfill all inclusion criteria. Patients consented but not meeting randomization criteria will not have any data collected or change to their management.

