#### (4) **Hour 3**

- a. Cardiac index (L/min/m^2)
- b. RAP (mmHg)
- c. PASP (mmHg)
- d. mPA (mmHg)
- e. PADP (mmHg)
- f. PCWP (mmHg)
- g. PAPi
- h. RSVWI (mmHg L m^-2)
- i. SVR (dynes/sec/cm^5)
- j. PVR (dynes/sec/cm^5)
- k. SBP/DBP/MAP
- l. API
- m. Standing weight
- n. Urine output
- o. Blood glucose taken from BMP
- p. HbA1c
- q. Current Vasoactive doses
- r. Renal function (serum Creatinine, serum eGFR)
- s. Total diuretic dose

(5) **Hour 27** - 2 hours after 2nd dose of SGLT2i, which will be administered 24 hours after first dose, or equivalent time period after which the dose would have been given for the No-SGLT2i arm.

- a. Cardiac index (L/min/m^2)
- b. RAP (mmHg)
- c. PASP (mmHg)
- d. mPA (mmHg)
- e. PADP (mmHg)
- f. PCWP (mmHg)
- g. PAPi
- h. RVSWI (mmHg L m^-2)
- i. SVR (dynes/sec/cm^5)
- j. PVR (dynes/sec/cm^5)
- k. SBP/DBP/MAP
- l. API
- m. Standing weight
- n. Urine output
- o. Blood glucose taken from BMP
- p. HbA1c
- q. Current Vasoactive doses
- r. Renal function (serum Creatinine, serum eGFR)
- s. Total diuretic dose

**(6) Hour 51 & Hour 75 - if vasoactives are still required and pulmonary artery catheter is still being used for routine clinical care**, we will continue SGLT2i for up to 4 doses, and the additional invasive hemodynamics repeated two hours after each dose will be collected.

- a. Cardiac index (L/min/m^2)
- b. RAP (mmHg)
- c. PASP (mmHg)
- d. mPA (mmHg)
- e. PADP (mmHg)
- f. PCWP (mmHg)
- g. PAPi
- h. RVSWI (mmHg L m^-2)
- i. SVR (dynes/sec/cm^5)
- j. PVR (dynes/sec/cm^5)
- k. SBP/DBP/MAP
- l. API
- m. Standing weight
- n. Urine output
- o. Blood glucose taken from BMP
- p. HbA1c
- q. Current Vasoactive doses
- r. Renal function (serum Creatinine, serum eGFR)
- s. Total diuretic dose

Leveled invasive hemodynamic measurements, standing weights, intake and outputs, blood glucose, blood pressure, vasoactive doses, and renal function will stop being collected for the

study after the fourth dose of SGLT2i, or equivalent timing for those randomized to the No-SGLT2i arm.

The leveled hemodynamic measurements measured via a pulmonary artery catheter at end expiration will be collected. A picture will be taken and shown to an Advanced HF attending not involved with the patient's current care and blinded to treatment for interpretation.

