The patient's participation in the study will end after completion of 4 doses of the SGLT2i or sooner if patient is transferred out of the CCU and continuous hemodynamic monitoring is discontinued, or if patient develops any of the safety end points as listed below. The physician will discuss the ongoing treatment plan with the patient at this point.

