## **Safety End Points**

1. Need for initiation of second vasoactive medication and/or MAP < 60
2. Development of acute kidney injury, based on eGFR value < 30ml/min/1.73m^2
3. Adverse events reflecting urinary tract infection, genital infection, bone fracture, and diabetic ketoacidosis

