## **Inclusion Criteria**

1. Age  $\geq$  18 years old
2. Reduced ejection fraction (HFrEF) of 40 or less
3. Estimated glomerular filtration rate (eGFR)  $> 30\text{ml/min}/1.73\text{m}^2$
4. Admitted to CCU by advanced heart failure service for decompensated heart failure requiring continuous hemodynamic monitoring with a pulmonary artery catheter

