## **Exclusion Criteria**

1. Diagnosis of type 1 DM
2. eGFR  $< 30\text{ml/min}/1.73\text{m}^2$
3. age  $< 18$  years old
4. Jehovah's witnesses
5. Diagnosis of group 1 pulmonary arterial hypertension
6. Insulin requirement above standard low dose sliding scale
7. Patients with a history of DKA
8. Allergies to SGLT2i medications
9. History of intolerance to SGLT2i medications
10. Patients listed for cardiac transplantation or on mechanical support
11. Pregnant or breastfeeding

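### Entry sections disagree on whether vasoactive support is required, and safety end point 1 counts a second vasoactive or MAP below 60 without reference to Hour 0 status

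*Combined protocol and SAP*

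**What the plan says.** All references are to the combined protocol and SAP.

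**Who is enrolled.** Study Subjects describes patients "admitted to the CCU by the advanced heart failure service after right heart catheterization for acute decompensated heart failure requiring vasoactive support". Inclusion criterion 4 reads "Admitted to CCU by advanced heart failure service for decompensated heart failure requiring continuous hemodynamic monitoring with a pulmonary artery catheter" and does not mention vasoactives. The eligibility paragraph under Study Design, Study Procedures, and Statistical Procedures agrees with the criterion: patients "determined to need pulmonary artery catheter in place for continuous hemodynamic monitoring following right heart catheterization, will be included in this study". The only exclusion that touches circulatory support is "Patients listed for cardiac transplantation or on mechanical support"; none concerns MAP or the number of vasoactive agents.

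**Later measurements.** In the schedule, Hours 51 and 75 apply only "if vasoactives are still required and pulmonary artery catheter is still being used for routine clinical care".

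**Safety end point 1.** Safety End Points lists "Need for initiation of second vasoactive medication and/or MAP < 60". It gives no baseline reference, start of observation or duration.

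**Consequence.** The paragraph that closes the schedule ends participation after the fourth dose, on leaving the CCU with monitoring discontinued, "or if patient develops any of the safety end points as listed below".

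**Data.** Blood pressure including MAP (item k) and current vasoactive doses (item q) are listed at Hour 0 and at Hours 3, 27, 51 and 75.

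**The concern.** The sections describe two different populations. A patient with a pulmonary artery catheter and no vasoactive agent fits the Inclusion Criteria but not Study Subjects, so two people screening from this protocol could enrol different patients.

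The safety end point adds to the problem. An ordinal such as *second* has a fixed meaning only if the number of agents at the start is known, and the criteria leave that number open. The same clinical event, one more agent than at Hour 0, would count in one patient and not in another.

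Two things are at stake. One is the reported count of this end point by arm. The other is the primary outcome data: because the end point also ends participation, the rule helps decide who contributes later cardiac index (CI) and PCWP values.

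**Working it through.** This point rests on comparing texts. The plan's 16 (PCWP) and 18 (CI) patients per arm cannot be reproduced, because no standard deviation is given, but nothing below depends on one.

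**Step 1. Apply each section to each possible Hour 0 status.**

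| Hour 0 status | Fits Study Subjects? | Fits Inclusion Criteria and design text? | How safety end point 1 behaves as written |
|---|---|---|---|
| No agent, MAP at least 60 | No | Yes | Starting a first agent does not count unless MAP is also below 60 |
| One agent, MAP at least 60 | Yes | Yes | Both parts work as a new event |
| Two or more agents, MAP at least 60 | Yes | Yes | A further agent is not a second one; only the MAP part can register |
| MAP below 60, any number of agents | Depends on agents | Not excluded | The value is already below the limit before the Hour 1 dose; its handling is not stated |

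The third row matters most. It holds under either description of the population, so settling the eligibility wording would not remove it.

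**Step 2. Check the Hour 51 and Hour 75 condition.** It asks whether vasoactives are *still* required. That fits Study Subjects. A patient enrolled under the Inclusion Criteria on no agent has nothing to continue requiring, so the mismatch also reaches the number of doses and measurements a patient contributes.

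**Step 3. Follow the consequence.** An escalation that is counted ends participation, and later CI and PCWP values are then not collected. An escalation that is missed does not end participation, so no outcome value is lost; only the safety count is wrong. For MAP below 60 at Hour 0, one reading ends participation before the first dose and the other lets the patient continue.

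**Step 4. Size.** With 20 per arm, one patient classified differently changes that arm's safety rate by 1/20 = 5 percentage points. The documents give neither the distribution of agents or MAP at Hour 0 nor a rate of early exits, so the expected number of such patients cannot be computed.

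**Step 5. Check whether a few exits would breach the sample size.** The stated 18 per arm for CI assumes equal arms. If three patients left one arm without usable data, the arms would be 17 and 20:

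- variance factor: 1/17 + 1/20 = 0.0588 + 0.0500 = 0.1088
- variance factor at 18 and 18: 2/18 = 0.1111
- equivalent equal arm size: 2 × 17 × 20 / (17 + 20) = 680/37 = 18.4

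The common standard deviation cancels from this comparison. 18.4 is above 18, so this pattern of loss keeps the stated CI power. PCWP needs only 16.

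**The case against.** The strongest reply is that the documents, read as a whole, mean new events in patients already on support. Study Subjects and the Hour 51 and Hour 75 condition both point to vasoactive support, so the silence of the Inclusion Criteria may be an omission from a list. Safety end point 1 speaks of *initiation*, and the paragraph on ending participation speaks of a patient who *develops* an end point. The study is a 40-patient pilot with no formal safety comparison.

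Much of this stands, and it rules out two stronger readings:

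- A reader might infer that a patient already on two agents meets the end point before dosing. The words *initiation* and *develops* speak against it. Prior satisfaction is arguable only for the MAP part, which carries no such word in Safety End Points, and even there *develops* argues against ending participation.
- A reader might infer that the plan assumes exactly one agent at Hour 0. It nowhere says so. The Hour 51 and Hour 75 condition uses the plural and presumes only some vasoactive use.

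The reply does not close the gap. If Study Subjects governs, the patient on no agent largely drops out of the problem, but the patient on two or more remains eligible and a further agent is still not counted. *Develops* implies a change, yet no reference status or start time is given against which to judge it. The absence of a formal test does not help either, since a reported count still needs a definition.

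**Conclusion.** The point holds as an internal inconsistency with a practical consequence. The sections do not agree on whether vasoactive support is an entry condition, and safety end point 1 lacks a reference to Hour 0. It therefore misses some escalations and leaves MAP below 60 at entry undefined.

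The size is unknown: 5 percentage points of an arm's safety rate per patient affected, with no rate in the documents. The effect on the primary outcomes is confined to exits before the analysed time. The Outcomes section names no such time, and Hour 3 values may already exist for patients who leave later.

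A reader might also infer that three early exits in one arm would take CI below its stated sample size. The documents do not support that: 17 against 20 is equivalent to 18.4 per arm, and a missed event removes no data at all.

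The conclusion assumes that patients on no agent, on two or more agents, or with MAP below 60 can occur. The written criteria allow this, but the documents do not say how often it happens.

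**What to change.** 1. The sponsor should reconcile the design text, Study Subjects, the Inclusion Criteria and the Hour 51 and Hour 75 condition, so that one statement on vasoactive support governs eligibility.
2. The sponsor should reconcile Safety End Points with the paragraph on ending participation, so that it is clear which event ends participation and how a condition present at Hour 0 is treated. Which population is intended and what ends participation are clinical decisions, and no rule is proposed here.
3. For the analysis only, report safety end point 1 relative to Hour 0: show each patient's number of agents and MAP at Hour 0 and at each later scheduled time, beside the count as written. Items k and q supply this, assuming doses are recorded separately for each agent.

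The cost is protocol wording and one table, with no added scheduled measurement. The downside is small: items k and q are listed only at the scheduled times, so a brief fall in MAP, or an agent started and stopped in between, would not be captured by them.

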## **Inclusion Criteria**

1. Age  $\geq$  18 years old
2. Reduced ejection fraction (HFrEF) of 40 or less
3. Estimated glomerular filtration rate (eGFR)  $> 30\text{ml/min}/1.73\text{m}^2$
4. Admitted to CCU by advanced heart failure service for decompensated heart failure requiring continuous hemodynamic monitoring with a pulmonary artery catheter

## **Exclusion Criteria**

1. Diagnosis of type 1 DM
2. eGFR  $< 30\text{ml/min}/1.73\text{m}^2$
3. age  $< 18$  years old
4. Jehovah's witnesses
5. Diagnosis of group 1 pulmonary arterial hypertension
6. Insulin requirement above standard low dose sliding scale
7. Patients with a history of DKA
8. Allergies to SGLT2i medications
9. History of intolerance to SGLT2i medications
10. Patients listed for cardiac transplantation or on mechanical support
11. Pregnant or breastfeeding

## **Recruitment**

Patients undergoing a right heart catheterization, either as outpatient or inpatient, who are determined to have a high likelihood of needing CCU admission for acute decompensated heart failure requiring continuous invasive hemodynamic monitoring with a pulmonary artery catheter, will be recruited by members of the Advanced Heart Failure team. Patients will be approached before sedation is given for the right heart catheterization procedure.

## **Informed Consent Process**

The consent process will take place during a routine visit or inpatient hospital stay. Patients will be given an informed consent and allowed as much time as needed to read all components and be provided time to formulate questions. If questions arise, the PI or a member of the research team will provide answers to the patient regarding participation in the research study. Family members or caretakers will also be encouraged to participate in the informed consent process if applicable.

Ample time will be given for the informed consent process. After a complete explanation of the study, the informed consent document will be reviewed. Subjects will be asked to verbalize their understanding of the study and encouraged to ask questions. Family members or caretakers will also be encouraged to participate in the informed consent process if applicable.

## **Confidentiality of Study Data and Privacy Protections**

Data will be abstracted into an electronic database. The database will be within the UCMC Department of Medicine, Section of Cardiology. The data will be password protected and covered by all of the firewalls and security features of the Department of Medicine. The data will

also be housed on a password protected encrypted laptop using University of Chicago standards per CBIS.

Once collected, an individual's data will not be available to anyone other than the investigators and study personnel involved in this project. The data will be abstracted and entered into an electronic database by a member of the research team. The database will be within the Department of Medicine, Section of Cardiology. The data will be password protected and covered by all of the firewalls and security features of the Department of Medicine. Name, address, email address, phone number and medical record number will be stored separately from the database. In the database, a code will be recorded with the data instead. Only the study staff will be able to link the code to the subject's name and other identifying information. The link to identifiers will be destroyed at the end of 6 years per HIPAA regulations.

### **Potential Risks**

SGLT2i have been shown to have beneficial effects on renal function (5,20). However, due to its direct effect on the kidneys, SGLT2i are labeled for patients with eGFR  $\geq 20\text{ml/min}/1.73\text{m}^2$  or GFR  $\geq 30\text{ml/min}/1.73\text{m}^2$  depending on the medication. Due to this, we will exclude patients with eGFR  $< 30\text{ml/min}/1.73\text{m}^2$ . Increased risk of genital mycotic infections (i.e. vaginitis and balanitis), urinary tract infections, pyelonephritis, urosepsis, and perineal necrotizing fasciitis have been reported, but only genital infections have been shown to be a significant risk in large randomized trials (3-5). Additionally, there has been a small increased risk of diabetic ketoacidosis associated with the use of SGLT2i, though this was predominantly in patients on insulin, who will not be included in this study (5). Lastly, canagliflozin was associated with an elevated risk of lower limb amputation and bone fractures compared to placebo in the CANVAS trial, but this was not seen with the CREEDANCE trial of canagliflozin, or in other SGLT2i randomized controlled trials, including the EMPA-REG OUTCOME, DECLARE-TIMI-58, DAPA-HF, EMPEROR-Reduced trials completed for empagliflozin and dapagliflozin (4). We will not be using canagliflozin in this study.

The adverse reactions of dapagliflozin in order of incidence include female genital mycotic infections, nasopharyngitis, urinary tract infection, back pain, increased urination, male genital mycotic infections, nausea, influenza, dyslipidemia, constipation, dysuria, pain in extremity, increase in creatinine, increase in hematocrit, dyslipidemia, hypersensitivity reactions, urosepsis, necrotizing fasciitis of the perineum.

Since patients are randomized to two routine care arms, we do not believe there is additional risk incurred by participating in this study. The treating physician will be notified of the randomization assignment and can override the assignment if they believe it to be in the best interest of the patient. While SGLT2 inhibitor therapy is approved for use in patients with HFrEF, there is not sufficient data guiding its use in the ICU-setting in patients with acute decompensated heart failure. If benefit is shown in the SGLT2i population, the arm without SGLT2i would lose the hypothesized benefit of renal and cardiovascular benefits during the CCU stay.

## **Data and Safety Monitoring**

Data safety measures will be maintained as above. Appropriate CBIS and risk management personnel will be contacted immediately if any data loss is suspected. All patients in this study are closely monitored throughout the duration of activity in this study as, by nature, they are in the CCU. Any study-related adverse events will be reported to the IRB according to the IRB's reporting requirements. Adverse events related to the SGLT2i will be reported to the manufacturer or directly to the FDA as would normally occur for safety reporting of routine medications.

40 subjects in this initial pilot study are followed for less than 4 days. We believe that this is the minimum required to clarify potential benefit of SGLT2 inhibitor therapy in the acute setting in patients with acute decompensated heart failure. We do not anticipate adequate data prior to study completion evidencing benefit that would justify study stoppage or redesign.

## **Potential Benefits**

SGLT2i data indicates improvement in cardiovascular outcomes, including cardiovascular death and heart failure hospitalization in patients with and without known heart failure (3-7). The proposed mechanisms of action of SGLT2i leading to these improved cardiovascular outcomes, specifically increased natriuresis and diuresis and reduced cardiac work and remodeling should have beneficial effects on patients with acute decompensated heart failure (9-11,13-17). Recently, it has been shown that SGLT2i decreased heart failure exacerbations and cardiovascular mortality regardless of a diagnosis of diabetes (6,7). To this end, the 2021 Heart Failure Treatment guidelines have updated its recommendations to include SGLT2i as standard of care. Therefore, it is hypothesized that the benefit of SGLT2i seen in HFrEF patients will also be effective in the acute setting in patients with acute decompensated heart failure.

## **Alternatives**

Participation is voluntary, and the alternative is not to participate in this study. Outside of the study, the decision whether or not the patient receives an SGLT2i would be based on the treating physician's discretion.

## **Research at External Sites:**

All research will be conducted at University of Chicago Medical Center (UCMC). This is not a multicenter study; thus, University of Chicago will be the only institution involved with the research.

